**Table 3. List of covariates**

Characteristic	MID-NET	Note/ Covariate assessment period
Age, mean (SD)	Yes	On index date
Race/ethnicity	No	Most of all is Japanese
Sex (Male, female)	Yes	On index date
Year of cohort entry	Yes	On index date
Lifestyle risk factors		The closest measurement taken within one year before the index date, including the index date itself.
Smoking index	Yes	This information might be only recorded when patients are admitted to the hospital.
Information of lab value		The closest measurement taken within one year before the index date, including the index date itself.
Height, cm, mean (SD)	Yes	
Weight, kg, mean (SD)	Yes	
Body mass index, mean (SD)	Yes	Calculated with height and weight, kg/m 
Serum creatinine, mg/dL, mean (SD)	Yes	
eGFR, mL/min/1.73 m 	Yes	% among three cohorts to be confirmed
Level of renal insufficiency a		Calculated with serum creatine level. Classified into four groups. >= 90 (Normal); 60 -< 90 (Mild); 30 -< 60 (Moderate); < 30 (Severe)
Fasting plasma glucose, mg/dL, Mean (SD)	Yes	
HbA1c, %, Mean (SD)	Yes	
HDL-C, mg/dL, Mean (SD)	Yes	
LDL-C, mg/dL, Mean (SD)	Yes	
Triglyceride level, mg/dL, Mean (SD)	Yes	
History of healthcare utilization		Within one year prior to index
Number of inpatient hospitalizations	Yes	
Number of outpatient visits	Yes	
Number of cardiovascular-related hospital days	Yes	
Number of serum creatinine tests	Yes	% among three cohorts to be confirmed
Number of lipid-related lab tests	Yes	% among three cohorts to be confirmed
History of fracture	Yes	All available history unless otherwise specified
Any fracture	Yes	
Vertebral fractures	Yes	
Hip fracture	Yes	

Characteristic	MID-NET	Note/ Covariate assessment period
History of fracture hospitalizations	Yes	
Osteoporosis diagnosis	Yes	
History of use of anti-osteoporosis drugs		All available history unless otherwise specified
Oral bisphosphonates	Yes	
IV bisphosphonates	Yes	
Anti-RANKL antibody (Denosumab)	Yes	
PTH analogs (Teriparatide or abaloparatide)	Yes	
Selective estrogen receptor modulators (Raloxifene, bazedoxifene)	Yes	
Estrogen replacement therapy	Yes	
Historical use of the medication that increased fracture or osteoporosis risk	Yes	Fracture/OP risk factors, Within one year prior to index
Anticonvulsant		
Antidepressant	Yes	
Antiparkinsonian	Yes	
Antipsychotic	Yes	
Benzodiazepine	Yes	
NSAIDs and COX-2 inhibitor	Yes	
Corticosteroids (oral or injectable)	Yes	
Opioids	Yes	
Proton-pump inhibitor	Yes	
History of other comorbidities that increased fracture or osteoporosis risk		Fracture/OP risk factors. Within one year prior to index
Rheumatoid arthritis	Yes	
Systemic Lupus Erythematosus	Yes	
Chronic obstructive pulmonary disease	Yes	
Asthma	Yes	
Pneumonia	Yes	
Parkinsonism	Yes	
Dementia	Yes	
Depression	Yes	
Schizophrenia	Yes	
Sepsis or septicemia	Yes	
Sleep apnea	Yes	
Vitamin D deficiency	Yes	
History of cardiovascular events		All available history unless otherwise specified
Myocardial infarction within 1 year prior to index	Yes	Within one year prior to index
Myocardial infarction $\geq$ 1 year prior to index	Yes	$\geq$ 1 year prior to index
CCI within 1 year prior to index	Yes	Within one year prior to index
CCI $\geq$ 1 year prior to index	Yes	$\geq$ 1 year prior to index
History of CV risk factors		Within one year prior to index
Atherothrombosis	Yes	
Heart failure	Yes	
Peripheral artery disease	Yes	

Characteristic	MID-NET	Note/ Covariate assessment period
Cerebrovascular disease	Yes	
Coronary artery disease	Yes	
Angina (including stable and unstable)	Yes	
Atrial fibrillation	Yes	
Conduction disorder	Yes	
Hypertension	Yes	
Hyperlipidemia	Yes	
Hypercholesterolemia	Yes	
Obesity	Yes	
Peripheral vascular disease	Yes	
Transient ischemic attack	Yes	
Type 2 diabetes mellitus	Yes	
CKD	Yes	
Chronic kidney disease (stage III, IV and V) without dialysis	Yes	
Chronic kidney disease (stage III, IV and V) with dialysis	Yes	
End stage renal disease	Yes	
History of cardioprotective therapies		Within one year prior to index
Diuretic		Antihypertensive
Beta-blocker		Antihypertensive
Calcium Channel blockers		Antihypertensive
Angiotensin Converting Emzyme (ACEI)/ Angiotensin Receptor Blockers (ARBs)	Yes	Antihypertensive
Insulin	Yes	Anti-diabetes
Metformin	Yes	Anti-diabetes
GLP-1 receptor agonists	Yes	Anti-diabetes
Thiazolidinediones	Yes	Anti-diabetes
Sulfonylureas	Yes	Anti-diabetes
SGLT- 2 inhibitors	Yes	Anti-diabetes
DPP- 4 inhibitors	Yes	Anti-diabetes
Statins (any kind)	Yes	lipid lower agents
Ezetimide	Yes	lipid lower agents
Statins + ezetimide combinations	Yes	lipid lower agents
PCSK9i	Yes	lipid lower agents
Other lipid lowering drugs (fibrates, gemfibrozil, Niacin, Cholestyramine)	Yes	lipid lower agents
Aspirin	Yes	Antiplatelets/ antithrombotic
Clopidogrel and other antiplatelet	Yes	Antiplatelets/ antithrombotic
Anticoagulants	Yes	Antiplatelets/ antithrombotic
Digoxin	Yes	Antiarrhythmic
Amiodarone and other antiarrhythmic	Yes	Antiarrhythmic
Antianginal nitrate	Yes	Antianginal agents
Antianginal ranolazine	Yes	Antianginal agents

a. To calculate eGFR please use below formula: For females:  $eGFR = 194 \times SCr^{-1.094} \times Age^{-0.287} \times 0.739$ ; For males:  $eGFR = 194 \times SCr^{-1.094} \times Age^{-0.287}$

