### **6.5 Feasibility and Futility Considerations**

We used publicly available data to determine the sample size in MID-NET. The effect estimate's confidence interval may have low precision because of the low event rate. We used the NDB open data to describe the challenge of measured and unmeasured confounders in this study, and followed the draft ICH M14 guidance "General Principles on Planning and Designing Pharmacoepidemiological Studies That Utilize Real-World Data for Safety Assessment of a Medicine" to perform bias analysis for study results interpretation. Given that MID-NET operates within a hospital-based setting and is currently inaccessible, we conducted feasibility assessments using Medical Data Vision (MDV) data to inform the choice of baseline period and the renal impairment level for protocol development. Amgen CfOR Data Analytics Center performed the internal analysis of MDV. The results suggest that sample size may not significantly increase even with a 3-month baseline period. In line with PMDA's recommendation, a 12-month period is set as the baseline for this study. In addition, the diagnosis of CKD stages did not have enough sensitivity to describe the level of renal impairment in the MDV data. Instead, using serum creatinine and estimated glomerular filtration rate (eGFR) can provide a more accurate and granular classification of renal insufficiency among osteoporosis patients. The MID-NET summary report I stated that more than 90% of patients who were given romosozumab (1908 out of 1989), alendronate (18,570 out of 19,118) or PTH analogs (2,978 out of 3,156) had their serum creatinine tested during 2021-2023 (PMDA, 2024a).

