#### **8.7.1.3 Secondary Analysis**

For secondary objective, we will use the same method that we used in primary analysis and restrict to a subset that have available information on renal insufficiency. Since romosozumab and oral alendronate have a warning for use in patients with creatinine clearance less than 30 mL/min/1.73 m^2, patients treated with these therapies may exhibit a lower prevalence of renal insufficiency compared to those treated with PTH analogs. To ensure the comparability between treatment groups, we will limit the analyses to patients with similar levels of renal function to mitigate potential bias. The subgroup analyses will be performed based on the following criteria: 1) no chronic renal disease (or eGFR  $\geq$  90 mL/min/1.73 m^2), 2) stage 1 or II CKD (or eGFR 60-89 mL/min/1.73 m^2), 3) stage III CKD (or eGFR 30-59 mL/min/1.73 m^2), or 4) stage IV or V (or eGFR < 30 mL/min/1.73 m^2).

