### **8.9.2 External Validity of Study Design**

Since MID-NET is a distributed data network system that serves as regional core hospitals with an emergency department, the population identified from this network may not be generalizable to those who visit primary care.

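### Renal strata rest on the single creatinine nearest the index date with no limit on care setting, so a value from an acute admission can put a patient in the wrong stratum

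*Protocol*

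**What the plan says.** In Protocol Table 3, the laboratory block has one selection rule: "The closest measurement taken within one year before the index date, including the index date itself". Level of renal insufficiency is then "Calculated with serum creatine level. Classified into four groups", with cut-offs at 90, 60 and 30, using the creatinine-based equation in the table's footnote. The rule has no condition on setting, repeat measurement or persistence.

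The Study Design Schema lists inpatient laboratory data among what MID-NET can observe, and section 8.3.3 places no setting limit on laboratory codes. Section 8.9.2 says the network "serves as regional core hospitals with an emergency department".

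Table 3 labels the bands normal, mild, moderate and severe. The chronic reading comes from the Abstract and section 8.7.1.3, where each band is paired with a CKD category, for example "stage IV or V (or eGFR < 30". These bands are the strata of the secondary objective, and section 8.7.1.3 gives their purpose: "we will limit the analyses to patients with similar levels of renal function to mitigate potential bias".

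Section 6.5 explains why eGFR is used instead of codes: "the diagnosis of CKD stages did not have enough sensitivity to describe the level of renal impairment in the MDV data". It does not discuss acute values. Codes for CKD, dialysis and end-stage renal disease appear in Table 3 as covariates only and do not confirm a band. Table 3 also lists "Number of serum creatinine tests" as a covariate, so repeat values are expected.

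**The concern.** A CKD stage describes a lasting state, and one creatinine drawn during an acute illness may not reflect it. In acute-care hospitals, the value nearest the start of an osteoporosis drug can come from a recent admission, for instance for a fracture or an infection, even when the drug itself is started as an outpatient.

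Safety in renal dysfunction is the important missing information named in section 6.2, and the secondary objective is built on these strata. Misplaced patients mix different levels of function within a stratum and blur any difference in risk between levels. The <30 stratum is the most exposed, because it is likely to be small and borders the much larger 30-59 group.

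**Working it through.** **1. The plan's own figure.** Section 6.5 says more than 90% of users had creatinine tested in 2021-2023. The counts agree: 1,908/1,989 = 95.9%, 18,570/19,118 = 97.1%, 2,978/3,156 = 94.4%. This is coverage by any test over that period. It does not show coverage within the one-year baseline window or the setting of the closest value.

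**2. Effect of a transient rise, from the protocol's formula.** eGFR is proportional to SCr^-1.094, so a k-fold rise divides eGFR by k^1.094. A patient falls below 30 if usual eGFR is below 30 × k^1.094:
- k = 1.5: 30 × 1.558 = 46.7
- k = 2: 30 × 2.135 = 64.0

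For a woman of 75 the formula puts eGFR 60 at 0.71 mg/dL and eGFR 30 at 1.35 mg/dL.

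**3. Size of the <30 stratum.** The documents do not give the share with eGFR <30; assume 2-10%. With section 8.5's 3,850 romosozumab patients and about 96% measured, the stratum holds 3,850 × 0.96 × 0.02 = 74 up to 3,850 × 0.96 × 0.10 = 370 patients. Table 4's rates and follow-up give 74 × 0.004 × 0.6 = 0.2 up to 370 × 0.01 × 0.8 = 3.0 expected events. Those are whole-cohort rates; the rate at low eGFR may be higher. Even so, a few misplaced patients could change this stratum's result.

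**4. How much acute values add.** Simulation of 2,000,000 patients; every input is an assumption. Usual eGFR is normal with mean 66 and SD 19, clipped to 8-130, which puts about 2.9% truly below 30. A single reading is usual eGFR × exp(error), with log SD 0.08 when stable. Acute readings were run three ways. *Wrong level* is the share of all patients in the wrong band. *Contamination* is the share of the observed <30 stratum whose usual eGFR is 30 or more. Increases over the no-acute row are in brackets, in percentage points.

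| Acute error | Share acute | Wrong level, % | Contamination, % |
|---|---|---|---|
| none | 0% | 13.7 | 13.5 |
| log SD 0.25, shift -0.10 | 10% | 16.3 (+2.6) | 22.7 (+9.2) |
| | 25% | 20.3 (+6.6) | 33.4 (+19.9) |
| | 40% | 24.3 (+10.6) | 41.7 (+28.2) |
| log SD 0.25, no shift | 10% | 16.2 (+2.5) | 18.7 (+5.2) |
| | 25% | 20.0 (+6.3) | 25.5 (+12.0) |
| | 40% | 23.7 (+10.0) | 31.5 (+18.0) |
| log SD 0.15, no shift | 10% | 14.8 (+1.1) | 15.1 (+1.6) |
| | 25% | 16.5 (+2.8) | 17.4 (+3.9) |
| | 40% | 18.2 (+4.5) | 19.7 (+6.2) |

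Monte Carlo error on contamination is a few tenths of a point.

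**5. What an outpatient preference recovers.** Suppose 25% of closest values are acute under the first error model, and half of those patients have no outpatient value. The closest-outpatient rule leaves 12.5% acute. Wrong level is linear in the acute share: 13.7 + 0.5 × 6.6 = 17.0%, against 20.3%. Contamination, rerun, is about 25% against 33%. The median of three outpatient values for every patient would give about 9% and 8%, but that is a ceiling, since many patients will not have three.

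**The case against.** The strongest reply is that the size is unsupported. The documents give neither the true share below 30, nor the share of acute closest values, nor how far such values deviate. With no acute values at all, a single reading still misplaces about 13-14%. With mild acute error the addition is small. Section 8.3.2 puts in-hospital use of the index drugs below 10%, which points to the lower end. All of this stands, with one limit: that figure is cited for event dating and does not exclude an outpatient start soon after discharge.

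Most misplacement is also near the boundary. At 10% acute under the harshest model, 22.7% of the <30 stratum has usual eGFR of 30 or more, but only 8.9% is at 35 or more and 5.3% at 40 or more. That is fair. With no acute values, however, the share at 35 or more is 0.6%, so the larger errors are the ones acute values bring.

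Section 8.7.1.1 plans a feasibility step covering creatinine and eGFR availability, and the SAP may refine the derivation. But the selection rule is already written in Table 3. The point concerns that stated rule, not missing detail.

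Finally, a value near the index date is defensible, because it reflects function when treatment was chosen, and a one-year median can be stale in a patient whose function is declining. This stands. It argues against replacing the closest value with a median throughout, or changing the other laboratory covariates. It does not argue against preferring outpatient values for the renal strata.

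**Conclusion.** The point holds as a weakness in a stated rule, and it should be changed. The rule admits acute inpatient values, and the Abstract and section 8.7.1.3 then read the bands as CKD stages. The mechanism follows from the protocol's own formula.

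The size is not known. If 10-40% of closest values are acute, they add about 1-11 percentage points to wrong level and about 2-28 points to contamination of the <30 stratum, over a baseline of about 13-14%. These ranges rest wholly on the assumed eGFR distribution, error sizes and acute shares.

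A reader might infer that the <30 stratum will be largely misclassified, or that the protocol deliberately calls for values from any setting. The documents support neither. The first needs an acute share they do not report. The second is an inference from the absence of a restriction together with observable inpatient laboratory data.

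**What to change.** In Table 3, for the secondary-objective strata, define renal level from the closest outpatient creatinine in the 365-day window up to and including the index date. Use an inpatient value only if no outpatient value exists, and flag those patients so that their number can be shown by cohort and stratum. Report two sensitivity analyses: the closest value in any setting, and the median of outpatient values where repeats exist.

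The cost is a wording change in Table 3 and one extra derivation on data already to be extracted. Appendix C places SAP completion in December 2025 and the start of analysis in January 2026, so the change fits before analysis. The drawbacks are a somewhat older value for some patients and remaining misclassification in those with inpatient values only. Ordinary single-reading noise also remains in the main definition; only the median analysis reduces it.

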## 6. Rationale and Background

### 6.1 Summary of the Medicinal Product of Interest

**Table 1. Summary of the Medicinal Product of Interest**

Date of Approval	08 January 2019
Date of Market Launch	04 March 2019
Therapeutic Classification	CCI
Re-examination Period	8 years
Approval Number	CCI
Brand Name	Evenity® Subcutaneous Injection 105 mg Syringes
Active Substance	Romosozumab
Dose and Formulary	Injection: Containing 105 mg of romosozumab in a prefilled syringe (1.17 mL).
Administration Route and Dosage	Adult: 210 mg of romosozumab once monthly for 12 months.
Indication	Osteoporosis in patients at high risk of fracture.
Conditions for Approval	The risk management plan should be developed and implemented as appropriate.

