### **8.3.3 Covariate Assessment**

Covariates that might influence osteoporosis treatment choice (ie, measures of prognosis) and are risk factors for various adverse events that could be assessed in safety evaluation are included to control for confounding. Sex, age and year of index date will be included as a covariate. All available historical data will be used to assess

history of fracture, history of pharmacologic therapy for osteoporosis, history for cardiovascular risk factor, history of cardioprotective therapies and or osteoporosis-related medication. Each covariate will be identified using a case ascertainment algorithm that incorporates individual or combinations of inpatient and outpatient ICD-10 diagnosis codes, drug codes, procedure codes, laboratory test codes, and date information from the MID-NET system. Covariates with a prevalence of 0.5% or less in the feasibility assessment within MID-NET will not be included in this study.

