## **8.7.2 Planned Method of Analysis**

### **8.7.2.1 General Considerations**

Given that MID-NET database is not accessible for now, descriptive analysis will be conducted prior to propensity score weighting portion of this study. To describe the incidence rate for outcomes, by romosozumab therapy, by PTH analogs, and by oral alendronate, the number of patients with events will be divided by person-time of follow-up. Incidence rate as well as hazard ratio will be accompanied by the corresponding 95% confidence intervals (CI) as a measure of precision.

We assume that measured and unmeasured confounding exist, and plan to perform a set of analyses to assess the comparability between treatment groups. Standardized mean differences (SMD) will be used to assess how different the baseline characteristics are between the treatment groups before and after propensity score weights are applied. We will consider the measured confounders with SMD values less than 0.1 as having negligible differences (Austin, 2009). In addition, negative control outcome analyses will be performed to rule out any potential unmeasured confounders (McGrath et al., 2020). For each negative control outcomes, risk difference and risk ratio in negative control outcomes will be calculated. The comparability of treatment groups will be explored by examining overall trends in effect estimates and the precision of CI across all negative control outcomes within an exposure contrast. We will assume there is significant uncontrolled confounding if the measure of association is not likely to be null.

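### Fracture history enters the propensity score with no recency split, so balancing ever-fracture does not ensure balance on recent fracture

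*Protocol*

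**What the plan says.** Section 8.3.3 gives the reason for choosing covariates: "Covariates that might influence osteoporosis treatment choice (ie, measures of prognosis) and are risk factors for various adverse events". For fracture history, among other histories, it states "All available historical data will be used to assess" them. Table 3 repeats this under its fracture heading: "All available history unless otherwise specified". The rows below it are any fracture, vertebral fracture, hip fracture and "History of fracture hospitalizations", and none of them specifies anything else.

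The block for prior cardiovascular events in the same table carries the same heading wording and then does specify. It has a row "Myocardial infarction within 1 year prior to index" and a companion row for one year or more, and it repeats the pair for a second, redacted event. Comorbidities, medicines and healthcare use, including "Number of inpatient hospitalizations", are limited to the year before index.

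Section 8.7.2.4 sends the Section 8.3.3 covariates into the propensity model. Section 8.7.2.1 sets the balance criterion for measured confounders: "SMD values less than 0.1 as having negligible differences". Table 1 gives the romosozumab indication as "Osteoporosis in patients at high risk of fracture".

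**The concern.** Fracture history is the covariate block closest to the indication, so by the protocol's own rationale it is a candidate confounder. Entered as ever/never, it gives the same value to patients whose fractures are weeks old and years old. Weighting can then equalise the share of patients with any past fracture while the share with a recent one still differs. The balance table would not reveal this, because it reports only listed covariates.

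If recent fracture is commoner in one arm and is also followed by a period of raised cardiovascular risk, the hazard ratio absorbs part of that risk. Follow-up starts at index and lasts at most one year, so a temporary excess soon after index would take up a material share of the person-time. The trial signal cited in Section 6.3 is 2.5% versus 1.9%, a ratio of 2.5/1.9 = 1.32, so even a modest bias matters for interpretation.

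**Working it through.** **1. The plan's own figure.** This point disputes no number in the protocol. Table 4 serves only as a scale. Its narrowest interval uses 3,850 romosozumab and 60,000 alendronate patients, a rate of 0.01 per person-year and 0.8 years:

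- Expected events: 3,850 × 0.01 × 0.8 = 30.8 and 60,000 × 0.01 × 0.8 = 480.
- SE of the log hazard ratio: √(1/30.8 + 1/480) = 0.186.
- 95% interval: exp(±1.96 × 0.186) = (0.69, 1.44). The protocol states (0.70, 1.45), so this agrees to within 0.01.

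**2. Inputs for the bias.**

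- From Section 8.5: mean follow-up of 0.6 or 0.8 years.
- Assumed, not in the documents: recent fracture in p1 = 30% to 50% of romosozumab starters and p0 = 20% of alendronate starters after weighting, with ever-fracture perfectly balanced.
- Assumed, not in the documents: recent fracture multiplies the cardiovascular rate by 2 or 3 for 90 days from index, and by 1 afterwards.

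**3. Average rate ratio over follow-up.** 90 days is 90/365.25 = 0.246 years. With everyone followed for the mean time T, the average ratio is R = 1 + (ratio − 1) × 0.246/T.

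**4. Apparent hazard ratio when the true value is 1.0.** Bias factor = [1 + p1(R − 1)] / [1 + p0(R − 1)].

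| Ratio in first 90 days | T (years) | R | 30% vs 20% | 50% vs 20% |
|---|---|---|---|---|
| 2 | 0.8 | 1.31 | 1.03 | 1.09 |
| 2 | 0.6 | 1.41 | 1.04 | 1.11 |
| 3 | 0.8 | 1.62 | 1.05 | 1.16 |
| 3 | 0.6 | 1.82 | 1.07 | 1.21 |

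Worked example for the last cell: (1 + 0.5 × 0.82)/(1 + 0.2 × 0.82) = 1.41/1.164 = 1.21. If p1 = p0, the factor is 1.00 whatever the ratio.

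**5. What the balance check would show.** Ever-fracture would have a standardized difference of 0. Recent fracture, if it were tabulated, would have:

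- 30% vs 20%: 0.10/√[(0.21 + 0.16)/2] = 0.23.
- 50% vs 20%: 0.30/√[(0.25 + 0.16)/2] = 0.66.

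Both are well above 0.1, but the planned table has no row in which they would appear.

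**6. Effect on the interval.** Multiplying the stated (0.70, 1.45) by 1.11 gives (0.78, 1.61). Multiplying it by 1.21 gives (0.85, 1.75).

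**The case against.** **Proxies exist.** The propensity model also holds admissions, outpatient visits, and opioid and NSAID use, all in the year before index. Together they carry some information on recency. A reader might infer that weighting cannot balance recent fracture at all. The documents do not support that; what stands is that balance is not ensured. The proxies are partial, because none of them separates a recent fracture from other reasons for admission or prescribing.

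**The causal premises are not in the protocol.** It gives high fracture risk as the indication. It does not say that recent fracture prompts romosozumab, or that cardiovascular risk rises for a time after fracture. The emergency role of MID-NET hospitals (Section 8.9.2) applies to all arms and so shows no difference between them. This objection stands in full: the premises, the direction and the size are assumptions and must be labelled so.

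**Other safeguards are planned.** The protocol expects unmeasured confounding and plans negative control outcomes, including trauma or injury admissions and dementia (Section 8.7.2.4), together with rule-out analysis and E-values (Section 8.7.2.5.3). These could detect or bound the bias, so it need not go unnoticed. They do not remove it, and fracture timing is something the study can measure: Section 8.3.3 says that covariate algorithms use date information.

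**It could be left to the SAP.** Section 8.7.1.1 leaves operational definitions to a feasibility step, and Section 8.9.3 leaves model building to the SAP. The look-back window for fracture is nevertheless fixed in the protocol, in both text and table, and the remark in Section 8.9.3 follows a passage on removing rare covariates. This is a stated choice rather than a gap.

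**Conclusion.** The structural point holds. Every fracture covariate is assessed over all history without a recency split, while the same table dates prior myocardial infarction. Balance on recent fracture is therefore neither ensured nor checked.

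Under the assumptions shown, a true hazard ratio of 1.0 against alendronate would appear as about 1.03-1.11 if risk doubles for 90 days, and about 1.05-1.21 if it triples. The calculation gives no credit to the partial proxies and starts the full 90 days at index, so it leans towards a larger bias for those inputs.

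Two stronger readings should be resisted:

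- A reader might infer that the hazard ratio is certainly biased upward. The direction follows only if recent fracture is commoner among romosozumab starters, which the documents do not show. Against PTH analogs the difference, and so the bias, may be smaller.
- A reader might apply a ratio of 2 or 3 to the whole of follow-up and get factors up to 1.25 or 1.43, the latter above the 1.32 trial ratio. That does not fit a risk that is raised only for a time. With a 90-day excess, the largest value in the range is 1.21.

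**What to change.** In Table 3, split fracture history by time before index, as is already done for myocardial infarction, and align the Section 8.3.3 text:

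- Split at least any fracture and fracture hospitalization; split hip and vertebral fracture where prevalence allows.
- Use, for example, within one year and one year or more, with a shorter most-recent window if numbers permit. The sponsor should set the exact windows. The 365 days of prior records required by Section 8.2.2.2 mean that the one-year window is available for every eligible patient.
- Include these terms in the propensity model for each pairwise comparison, and report their standardized differences against the 0.1 criterion.

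The cost is small. Splitting all four items in two adds four terms, and splitting them in three adds eight. They enter the treatment model, which rests on about 3,850 expected romosozumab patients, rather than on the roughly 9 to 31 romosozumab events implied by Section 8.5 (3,850 × 0.004 × 0.6 = 9.2; 3,850 × 0.01 × 0.8 = 30.8). Weights may become slightly more variable. Fractures treated outside the network will still be missed, and narrow windows for single sites may fall under the protocol's 0.5% prevalence rule. Appendix C schedules SAP completion for December 2025 and the start of analysis for January 2026, so the change can be settled before results are seen.
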